### 13.3. Adverse Events of Special Interest

Characteristics (e.g., number of occurrences, action taken, grade, etc.) of AESI (also referred to as immune-related adverse event, see Appendix 11 in protocol) will be summarized separately.

In addition, AESI will be listed separately.

### 13.4. Deaths and Serious Adverse Events

In the event that a subject has withdrawn consent, no data after the withdrawal of consent date from this subject including death is supposed to appear in the database, which should be part of the data cleaning process. All deaths will be summarised based on the number and percentage of subjects. This summary will classify subjects and primary cause of death as collected on the eCRF. A supportive listing will be generated to provide subject-specific details on subjects who died.

Summaries related to SAEs are specified in [Section 13.2](#).

SAEs are included in the listing of all adverse events. Separate supportive listings with subject-level details will be generated for

- Fatal SAEs
- Non-Fatal SAEs.

### 13.5. Adverse Events Leading to Discontinuation of Study Treatment and/or Withdrawal from the Study and Other Significant Adverse Events

AEs Leading to Discontinuation of Study Treatment will be summarized separately in descending order of total incidence by PT only and separate supportive listings will be generated with subject level details for those subjects:

- AEs leading to discontinuation of study treatment
- AEs leading to withdrawal from the study

### 13.6. Pregnancies

While pregnancy itself is not considered to be an AE or SAE, any pregnancy complication or elective termination of a pregnancy for medical reasons will be recorded as an AE or SAE as described in the protocol. If female subjects or female partners of male subjects become pregnant while on the study, the information will be included in the narratives and no separate table or listing will be produced.

### 13.7. Clinical Laboratory Evaluations

The assessment of laboratory toxicities will examine the following laboratory tests:

**Clinical Chemistry:** Total bilirubin, Aspartate aminotransferase (AST), Alanine aminotransferase (ALT), Alkaline phosphatase, Total protein, Albumin, Sodium, Potassium, Calcium, Urea/Blood Urea Nitrogen (BUN), Creatinine, Creatinine Clearance, and Glucose.

**Hematology:** Hemoglobin (HGB), Hematocrit (HCT), Platelet count, Red Blood Cell (RBC) count, White Blood Cell (WBC) count, Neutrophils (Absolute), Lymphocytes (Absolute), Monocytes (Absolute), Eosinophils (Absolute), Basophils (Absolute),

Neutrophils (%), Lymphocytes (%), Monocytes (%), Eosinophils (%) and Basophils (%); RBC indices (MCV and MCH).

**Thyroid Function Test:** Thyroid-stimulating hormone (TSH) and free thyroxine (T4 and T3) test.

**Urinalysis:** pH, Microscopic examination, Specific gravity, Ketones, Protein, and Glucose, Blood.

**Hepatitis Screening:** Hepatitis B (HBsAg) and Hepatitis C (Hep C antibody).

**Pregnancy Screening:** Serum  $\beta$ -hCG pregnancy test (as needed for women of child bearing potential).

Laboratory grades will be reported using the NCI-CTCAE v4.0.

Summaries of lab data by maximum toxicity grade will be provided.

Summaries of worst case grade increase (including unscheduled assessments) from baseline grade will be provided for all the lab tests that are gradable by NCI-CTCAE v4.0. These summaries will display the number and percentage of subjects with a maximum post-baseline grade increasing from their baseline grade. Any increase in grade from baseline will be summarized along with any increase to a maximum grade of 3 and any increase to a maximum grade of 4. Missing baseline grade will be assumed as grade 0. In addition, the summary will include grade increase from baseline by scheduled visits. For laboratory tests that are graded for both low and high values, summaries will be done separately and labeled by direction, e.g., sodium will be summarized as hyponatremia and hypernatremia.

Separate summary tables for hematology and clinical chemistry laboratory tests will be produced.

A supporting listing of abnormal urinalysis data will be provided.

Unless otherwise specified, the denominator in percentage calculation at each scheduled visit will be based on the number of subjects with non-missing value at each particular visit.

### **13.7.1. Analyses of Liver Function Tests**

Summaries of hepatobiliary laboratory events including possible Hy's law cases will be provided in addition to what has been described above.

A plot of maximum total bilirubin versus maximum ALT will be generated. A trellis display of LFT shifts from baseline to maximum values will be provided. A matrix display of LFT results will also be produced.

## 13.8. Other Safety Measures

Unless otherwise specified, the denominator in percentage calculation at each scheduled visit will be based on the number of subjects with non-missing value at each particular visit.

### 13.8.1. Vital Signs

Values of vital signs will be listed. The categories defined in [Section 10.3.3](#) will be flagged in listings.

### 13.8.2. Performance Status

ECOG performance status will be summarized at baseline and each post-baseline scheduled visit. Summaries will use frequency and percentage of subjects at each planned assessment time. A summary of change from baseline by scheduled visits will be performed, as well as the worst case post-baseline and the best case post-baseline changes during the study (improved, no change, deteriorated).

A supporting listing will also be provided.

### 13.8.3. ECG

For numerical values measured in triplicate, averages at each visit will be the basis of analysis summaries.

The QTc values based on Fridericia formula (QTcF) will be rounded to the integer and the values will be categorized into the ranges identified in [Section 10.3.2](#).

The changes in QTc values will be categorized into the clinical concern ranges which are specific to changes in QTc: 31-60 and >60 msec. Similarly, categories identified for PR interval and QRS interval will also be reported.

Listings of abnormal ECG findings and a listing of ECG values will be provided with PCS records flagged.

## 14. HEALTH OUTCOMES ANALYSES

No health outcomes analyses were planned for the study.

## 15. PHARMACOKINETIC ANALYSES

Statistical analysis of GSK3174998 and pembrolizumab pharmacokinetic parameters will be performed by, or under the direct auspices of, Oncology Quantitative Sciences (Statistician), GSK or Merck.

## 15.1. Drug Concentration Measures

PK analysis of GSK3174998 and pembrolizumab drug concentration-time data will be conducted by non-compartmental methods under the direction of CPMS, Quantitative Sciences, GSK or Merck.

Drug concentration-time data will be listed for each subject and summarized by descriptive statistics at each time point by cohort.

## 15.2. Deriving and Summarizing Pharmacokinetic Parameters

For the calculation of individual pharmacokinetic profiles, if one or more non-quantifiable (NQ) values occur in a profile before the first measurable concentration, they will be assigned a value of zero concentration. For linear plots, zero concentration value(s) before the first measurable concentration will be included in the plot. For log-linear plots, zero concentration value(s) before the first measurable concentration will be assigned a missing value.

If a single NQ value occurs between measurable concentrations in a profile, the NQ should generally be omitted (set to missing) in the derivation of pharmacokinetic parameters, statistical analysis, and the individual subject plots. If two or more NQ values occur in succession between measurable concentrations, the profile will be deemed to have terminated at the last measurable concentration prior to these NQs.

For the purpose of individual subject plots, these NQs will be set to 0, and the subsequent measurable concentrations will be retained. For the derivation of pharmacokinetic parameters, these NQs and any subsequent measurable concentrations will be omitted (set to missing).

NQs which occur after the last measurable concentration will be omitted (set to missing) in the derivation of pharmacokinetic parameters and from the individual subject plots. In some circumstances, there may be a pharmacokinetic rationale for fluctuation resulting in non-measurable concentrations in the middle of the concentration-time profile (e.g., entero-hepatic recycling, erratic absorption from transdermal/inhaled formulations). In these cases, the NQ values could be set to missing or to some other values (e.g.,  $\frac{1}{2}$  LLQ) and subsequent valid concentrations may be retained. A reference line indicating LLQ will be included in plots.

For the calculation of mean or median pharmacokinetic profiles, when estimating the mean or median value for the concentration at a given time point (i.e., descriptive mean or median curve), the following guidelines should be considered:

All NQ values will be set to zero except when an individual NQ falls between two quantifiable values, in which case it will be omitted from the calculation of mean or median profiles. Measurable concentrations which follow more than one consecutive mid-profile NQ will be omitted (set to missing).

The mean/median value at a time-point where one or more samples have NQ values will be reported (in tabular or graphical fashion) even if the mean/median value is below the

LLQ of the assay. For linear plots, zero concentration value(s) will be included in the plot. For log-linear plots, zero concentration value(s) will be assigned a missing value. Zero mean or median values will be included in summary tables. PK concentration values will be summarized.

The pharmacokinetic parameters will be calculated by standard non-compartmental analysis according to current working practices. All calculations of non-compartmental parameters will be based on actual sampling times. The following PK parameters will be determined if data permit:

- $C_{max}$
- $C\tau$
- area under the plasma concentration-time curve  $AUC(0-\tau)$  (repeat dosing)
- apparent terminal phase elimination rate constant ( $\lambda_z$ )
- apparent terminal phase half-life ( $t^{1/2}$ )
- systemic clearance of parent drug (CL)
- steady-state volume of distribution (Vss)

All derived PK parameters will be listed. For each of these parameters, the following summary statistics will be calculated for each dose level: median, minimum, maximum, arithmetic mean, 95% confidence interval for the arithmetic mean, standard deviation, coefficient of variation ( $CV = \sqrt{\exp(SD^2) - 1} * 100$  [NOTE: SD = SD of log transformed data]), geometric mean, 95% confidence interval for the geometric mean and standard deviation of logarithmically transformed data. The first point, last point and number of points used in the determination of  $\lambda_z$  will be included on the listing of the derived parameters. All PK parameters will be reported to at least 3 significant digits, but to no more significant digits than the precision of the original data.

### **15.3. Statistical Analyses**

There's no statistical analysis planned on PK data.

### **15.4. Population Pharmacokinetic Analyses**

Population PK analyses may be conducted under the direction of CPMS, Quantitative Sciences, GSK. The data from this study may be combined with the data from other studies for a population PK analysis, which may be reported separately.

## **16. PHARMACODYNAMIC AND BIOMARKERS ANALYSES**

### **16.1. Pharmacodynamic and Biomarker Analyses**

Receptor occupancy data will be summarized and plotted.

Other biomarker data may be reported separately from the main clinical study report, generated by GSK biomarker team if applicable. All endpoints of interest from all

comparisons will be descriptively and/or graphically summarized as appropriate to the data.

## 16.2. Immunogenicity Analyses

Serum samples will be collected and tested for the presence of antibodies that bind to GSK3174998 and pembrolizumab. Serum samples for testing anti-GSK3174998 and anti-pembrolizumab antibodies will be collected as described in the Time and Events schedule (protocol Section 7.1). The actual date and time of each blood sample collection will be recorded. Details of blood sample collection (including volume to be collected), processing, storage, and shipping procedures are provided in the SRM.

The timing and number of planned immunogenicity samples may be altered during the course of the study, based on newly-available data to ensure appropriate safety monitoring. In the event of a hypersensitivity reaction that is either 1) clinically-significant in the opinion of the investigator, or 2) leads to the subject withdrawing from the study, blood samples should be taken from the subject for immunogenicity testing at the time of the event and again 30 days, 12 weeks, and 24 weeks after. For subjects who prematurely withdraw from the study, immunogenicity testing will occur at withdrawal and at follow-up 30 days, 12 weeks, and 24 weeks after the last dose.

Serum will be tested for the presence of anti-GSK3174998 antibodies using the currently approved analytical methodology using a tiered testing schema: screening, confirmation and titration steps. The presence of treatment emergent ADA will be determined using a GSK3174998 bridging style ADA assay with a bio-analytically determined cut-point determined during assay validation. Samples taken after dosing with GSK3174998 that have a value at or above the cut-point will be considered treatment-emergent ADA-positive. These ADA positive samples will be further evaluated in a confirmatory assay, and confirmed positive samples will be further characterized by assessment of titer. Number and percentage of subjects with confirmed positive immunogenicity at each visit will be summarized. Denominator for the percentage is number of subjects with non-missing Screening, Confirming or Titer results at each visit. Results of anti-GSK3174998 antibody testing will be listed.

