9.4.2.4. Immunogenicity Analyses

Serum samples will be tested for the presence of anti-GSK3174998 antibodies using the currently approved analytical methodology using a tiered testing schema: screening, confirmation and titration steps. The presence of treatment emergent ADA will be determined using a GSK3174998 bridging style ADA assay with a bio-analytically determined cut-point determined during assay validation. Samples taken after dosing with GSK3174998 that have a value at or above the cut-point will be considered treatment-emergent ADA-positive. These ADA positive samples will be further evaluated in a confirmatory assay, and confirmed positive samples will be further characterized by assessment of titer. Results of anti-GSK3174998 antibody testing will be reported at the end of the study and will include incidence and titer. The presence or absence of antibodies to GSK3174998 in dosed subjects will be analyzed, then summarized descriptively and/or graphically presented.

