### **10.2.9. Multiple Assessments**

All data will be reported according to the nominal visit date for which it was reported (that is, no visit windows will be applied during dataset creation). Unscheduled data will only be included in the display sections that report worst-case. For summaries that collapse data across multiple planned time intervals, the worst-case data at each collapsed interval will be selected.

If multiple assessments on different days are reported for the same scheduled assessment, then the latest assessment for that scheduled assessment will be analyzed.

If multiple assessments are reported on the same date for the same scheduled planned time, then the worst-case result will be analyzed, with the exception of laboratory data reported from both central and local laboratories.

Furthermore, as quantitative ECG values will be measured in triplicate: 3 assessments are collected for each scheduled planned time, the first 3 measures will be used to compute the mean values for ECG intervals at each scheduled planned time.

For vital signs, three readings of blood pressure (BP) and pulse rate will be taken and the first reading will be discarded. The second and third readings will be averaged and recorded on eCRF to give the measurement reported at each time point.

Data from all assessments (scheduled and unscheduled), including multiple assessments, will be included in listings.

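### The SAP calls post-dose ADA treatment-emergent without using the pre-dose sample and tabulates ADA only by visit, so the subject-level secondary endpoint has no specified estimate

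*SAP*

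**What the plan says.** SAP 2.1 makes immunogenicity a secondary objective in both parts. The endpoint counts subjects who develop detectable ADA, as a number and a percentage. In Part 2 the objective covers both GSK3174998 and pembrolizumab.

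SAP 16.2 sets the positivity rule: "Samples taken after dosing with GSK3174998 that have a value at or above the cut-point will be considered treatment-emergent ADA-positive". Such samples go on to a confirmatory assay and then to titration. The planned table follows: "Number and percentage of subjects with confirmed positive immunogenicity at each visit will be summarized". Its denominator is also given: "Denominator for the percentage is number of subjects with non-missing Screening, Confirming or Titer results at each visit". The one other ADA output is a listing: "Results of anti-GSK3174998 antibody testing will be listed".

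Protocol 9.4.2.4 has the same positivity rule but commits to more in the report: "Results of anti-GSK3174998 antibody testing will be reported at the end of the study and will include incidence and titer". It adds: "The presence or absence of antibodies to GSK3174998 in dosed subjects will be analyzed, then summarized descriptively and/or graphically presented".

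Protocol Table 14 schedules a Day 1 pre-dose ADA sample for anti-GSK3174998 and, in Part 2, for anti-pembrolizumab antibodies.

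**The concern.** To *develop* ADA is to go from not having it to having it. That needs each subject's status before dosing and a view across all later samples. SAP 16.2 uses neither. Its emergence rule looks only at whether the sample was drawn after dosing, and its table looks at one visit at a time.

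If the plan is followed exactly, the study report would have a set of visit percentages that mix antibody present before dosing with antibody that appeared on treatment. It would have no figure for the named endpoint or for the incidence promised in the protocol. Someone would then have to choose a derivation after seeing the data, including how to treat subjects positive at baseline and those who crossed over from Part 1.

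**Working it through.** The documents give no ADA rate, target or sample size for this endpoint in their current text, so there is no plan figure to reproduce. The check sets the passages side by side and adds a counting illustration with assumed inputs.

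1. **What the endpoint needs.** It needs a baseline status for each subject, a count of subjects positive at any post-dose sample, and one common denominator.

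2. **What SAP 16.2 supplies.** The rule uses no baseline status. The table gives confirmed positives per visit, with a denominator that changes by visit. Visit counts cannot be joined afterwards: the number of subjects positive at any visit lies between the largest single-visit count and the sum of the visit counts, and the table does not show the overlap.

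3. **Illustration (all inputs assumed).** Take 60 subjects, six post-dose visits and no dropout. Let *b* subjects be positive before dosing and at every later visit. Let *e* subjects be negative before dosing and positive at exactly one visit, spread evenly over the six.
   - Target: *e*/60.
   - Any post-dose positive, baseline ignored: (*b* + *e*)/60. The SAP does not plan this figure; it is shown only to isolate the effect of ignoring baseline.
   - Average by-visit percentage: (*b* + *e*/6)/60.

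| *b* | *e* | Target | Any-time, baseline ignored | By-visit |
|---|---|---|---|---|
| 0 | 18 | 18/60 = 30.0% | 18/60 = 30.0% | 3/60 = 5.0% |
| 3 | 18 | 30.0% | 21/60 = 35.0% | 6/60 = 10.0% |
| 6 | 18 | 30.0% | 24/60 = 40.0% | 9/60 = 15.0% |
| 12 | 18 | 30.0% | 30/60 = 50.0% | 15/60 = 25.0% |
| 12 | 3 | 3/60 = 5.0% | 15/60 = 25.0% | 12.5/60 = 20.8% |

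   On a common denominator, ignoring baseline can only add subjects or leave the count unchanged. Looking at one visit instead of all can only miss subjects or leave the count unchanged. The by-visit figure is below the target in the first four rows and above it in the last. Visit-specific denominators add a further effect of unknown sign.

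4. **Samples outside the schedule.** For certain hypersensitivity reactions SAP 16.2 says "blood samples should be taken from the subject for immunogenicity testing at the time of the event", with further samples up to 24 weeks later. It also asks for a 24-week sample in subjects who withdraw early. The last column of Table 14 is 12 weeks after treatment. SAP 10.2.9 says "Unscheduled data will only be included in the display sections that report worst-case", and the ADA table is not a worst-case display. Read together, these samples may miss the table. This is an inference, not a statement in the SAP.

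5. **Second analyte.** The positivity rule and the listing in SAP 16.2 name only anti-GSK3174998. The by-visit sentence is not limited to one agent, but no anti-pembrolizumab rule or listing is given.

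6. **Crossover subjects.** Protocol 2.3.5 reports three subjects who moved from monotherapy to the combination. Their Part 2 pre-dose sample already follows GSK3174998 dosing. The general baseline definition in SAP 10.2.7 does not say which first dose counts for them.

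**The case against.** - **The emergence label is a screening-level label, and the table counts confirmed positives.** This stands: the label does not set the table's numerator. But confirmation shows that antibody is present, not that it is new.
- **Day 1 is a scheduled ADA visit, so pre-dose prevalence may appear in the table.** This may be so. It would be an aggregate figure, not linked to each subject's later status.
- **SAP 10.2.7 already defines baseline.** SAP 16.2 does not invoke it for ADA, and it leaves the crossover subjects open.
- **The listing allows the figure to be derived.** This stands for anti-GSK3174998, since SAP 10.2.9 puts unscheduled results in listings. The derivation is not defined, and no listing is named for anti-pembrolizumab.
- **Separate dataset specifications (SAP 10.2) may hold a baseline flag.** They are not among the documents, so this cannot be excluded. But SAP 1 presents the plan as covering all analyses needed for the study report, and it names no subject-level ADA summary.
- **The protocol shares the problem.** This stands in part. The missing baseline comparison and the missing anti-pembrolizumab rule are also in Protocol 9.4.2.4, and that section does not say that incidence means at any time. Only the missing incidence summary is specific to the SAP.
- **A sample taken at a reaction could fall on a dosing day with a scheduled ADA visit and enter the table.** This is fair, and is why exclusion of these samples is put only as a possibility.

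**Conclusion.** Wrong as written, and minor. Followed exactly, SAP 16.2 does not separate ADA present before dosing from ADA that develops, and it produces no any-time figure per subject. The secondary endpoint and the protocol's promised incidence are left without a specified estimate. This rests on the text alone and holds whatever the unseen dataset specifications derive, unless they also define the missing output.

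The size and net direction of any bias are unknown. A reader might infer that reported immunogenicity will be overstated because pre-existing antibody is counted. The documents do not support that: the by-visit table can also understate, and no baseline prevalence is given. A reader might also infer that the endpoint is lost. It is not, at least for anti-GSK3174998, because the listed results allow it to be recovered. The endpoint is descriptive and enrolment is closed, which keeps the consequence small.

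**What to change.** Revise SAP 16.2, and record whether the change aligns with or departs from Protocol 9.4.2.4:

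- Define baseline ADA from the Day 1 pre-dose sample, and state which sample is baseline for the three crossover subjects.
- Define treatment-emergent ADA as a negative baseline with at least one confirmed post-dose positive. State whether a titer rise from a positive baseline also counts.
- Report baseline prevalence and any-time subject-level incidence, counting unscheduled and event-driven samples, among subjects with a baseline and at least one post-dose result. Use the display groups already set in SAP 8.1.
- Keep the by-visit table as supportive.
- Give the same rule, summary and a listing for anti-pembrolizumab ADA in Part 2.

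The cost is SAP wording, one subject-level table per analyte and one extra listing. It uses samples already scheduled or required, and SAP 11.3 already identifies the re-enrolled subjects in a listing.
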